6.6 Samples

Remote DBS samples will be sent by participants directly to the University of Birmingham Clinical Immunology Service (UOB CIS). In-person samples will be transported to the local research laboratory at UoB, Southampton, Oxford or Imperial for processing. Samples will be transported between the sites under an appropriate material transfer agreement / collaboration contract. To enable this, consent will be obtained from participants for data collection, transfer and storage of all samples.

The following samples will be taken for the in-person cohort:

- 60ml of blood taken by venepuncture
- Saliva 4-minute passive drool into a universal
- Nasal secretions synthetic absorptive matrices (SAM) inserted in nostrils for 60 seconds

The samples taken for this study will be used as follows:

In-person sampling (n=400)		Remote sampling (n=2600)			
60ml of peripheral venous blood at each visit		Finger prick	er prick blood test at each remote visit		
Cells	Stored as peripheral blood lymphocytes to undertake T cell ELISpots and other exploratory studies.	Finger prick blood test	A capillary sampling method where the blood drop from a finger prick made by a lancet, is dripped onto a filter card. This is then dried (dry blood spot or DBS) and eluted in the laboratory and used to measure antibodies but can be used for other analytes.		
Serum/plasma Enumerate and characterise the antibody responses and storage for other exploratory studies.					
Mucosal sample	es				

Saliva	Measure antibody in saliva and compare this with serum to determine whether saliva could be used an alternative sample		
Nasal sections	for antibody testing. Measure antibody in nasal secretions and compare this with serum and saliva to determine whether could be used an alternative sample for antibody testing.		

A description of the sample transport to the laboratory and processing and distribution is described in the laboratory manual.

The samples will be stored for up 10 years from the last recruitment date for further ethically approved studies.

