9.3 Antigen specific T-cell response

Antigen-specific T-cell responses will be explored. Testing will include the key laboratory assay used is an established and standardised IFNy ELISpot assay (Oxford, Southampton), and through other immunologic assays.

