9.4 Sample Storage

Samples will be processed at Birmingham, Southampton, Oxford, and Imperial. To reduce transfer of samples they will remain within the processing laboratory according to the Health and Safety Executive (HES) license. Samples will be transferred between the laboratories for analysis during the study. The Clinical Immunology Service at the University of Birmingham is an ISO15189 UKAS accredited laboratory and will then centralise and store any remaining samples for the remainder of the study. Samples will be retained for 3 years following completion of the study to enable repeat

testing or for other ethically approved studies. This includes acellular and cellular material. At the end of this time samples will be stored in a licensed tissue bank. Samples will be labelled with the participants unique study identification, year of birth and initials; laboratory staff will be unable to identify participants from this information. Only authorised personnel will have access to the REDCap.

Samples will be processed at Birmingham, Southampton, Oxford, and Imperial. To reduce transfer of samples they will remain within the processing laboratory according to the Health and Safety Executive (HES) license. Samples will be transferred between the laboratories for analysis during the study. Samples will be retained for 3 years following completion of the study to enable repeat testing or for other ethically approved studies. This includes acellular and cellular material. At the end of this time samples will be stored in a licensed tissue bank. Samples will be labelled with the participants unique study identification, year of birth and initials; laboratory staff will be unable to identify participants from this information. Only authorised personnel will have access to the REDCap.

All freezers used in this study will be monitored for temperature controlled. Freezers are in rooms that require passcard or passcode access which is only granted to relevant members of the team. Storage of the samples will be pseudo-anonymised using three identifiers: by trial sample number, initials, and year of birth. This record will be kept at each laboratory information management system. Samples will be identified by barcodes generated within the laboratory and linked to the pseudo-anonymised record. Samples will be stored for up to 10 years in the so that repeat or further testing can be performed.

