9.5 Adverse event planning in the laboratory

The majority of samples will be processed and tested in the Clinical Immunology Service (CIS) at the University of Birmingham. The CIS provides NHS services to the NHS and has been accredited by UKAS. The governance process used for research in the CIS conforms with UKAS standards. Adverse events in the laboratory will be addressed according to the quality manual and accredited standard operating procedures. A STRAVINSKY laboratory manual will be used to ensure standardised procedures across all 4 laboratories.

Loss or damage to sample or samples not provided with 3 identifiers will be rejected and reported as a study violation. As with an NHS sample, the clinician or the PI will be contacted and if appropriate (timing of sample may make repeat request inappropriate) the participant will be contacted to explain and offer another appointment if they would be prepared to offer a further sample.

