Assuming serology is predictive of outcome, we will build a model to explore the predictive value of key patient data and the added value of serological results. We will explore the discrimination and calibration of a model only including baseline and behavioural variables compared to this model also including serological response. Discrimination will be determined by Harrell's C statistic and calibration will be determined by the predicted probabilities for infection. It is not possible to externally validate this model in this study; instead 1000 bootstrapped samples will be used in determining the 95% confidence intervals for the C statistic.

As a sensitivity analysis we will also consider serological response as a continuous variable. We will also consider time to first infection as a time to event outcome with death as a competing risk. This will be implemented in Stata using the *stcrreg* command. The same covariates will be included in the adjusted model as for the primary analysis. Unadjusted and adjusted analyses will present hazard ratios with 95% confidence intervals.

To assess the additive value of serological responses to CV status in predicting severe outcome We will undertake an analysis using the same modelling approach as for the primary outcome but with a composite outcome of severe infection (infection, hospitalisation or death).

Secondary Outcomes

To evaluate the serological vaccine responses of CV patients to new vaccines

28-day post vaccine (Visit 3) IgG antibody levels (BAU/ml) will be reported in HC and CV individuals. The proportion of combined and individual CV groups with no, low or normal Visit 3 antibody levels will be reported.

The median (IQR) of Visit 3 antibody levels in each CV group will be reported, alongside the values for HC.

Logistic regression models will be used to assess factors that contribute to serological response as a binary outcome with normal compared to lack of response (no/low). The model will include the baseline variables set out in **Section 5.2** and further variables may be added to the model if evidence emerges that such variable impacts on vaccine responses to vaccines. Univariable logistic regression will be used to explore the unadjusted relationship of each variable with the outcome and multivariable logistic regression will be used to explore the independent relationship of each variable with the outcome. We will report odds ratios and 95% confidence intervals for all models.

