- ii) Functional antibody assays e.g. live virus neutralisation and others (Oxford, Southampton)
- iii) Mucosal secretion serology on the MSD platform to monitor mucosal immunity (Birmingham) \square IgG and IgA quantification on samples from Visit 2 and Visit 3. Logistic regression analysis will be used to study the association between mucosal antibody titres and serum/plasma antibody titres, infection episodes and hospitalisation.

Descriptive analysis of these assays will be performed, statistical assessment will include, but will not be limited, to the following analyses:

C) To evaluate cellular responses to new vaccines in CV patients

28-day post vaccine (Visit 3) T-cell responses will be reported in HC and 400 CV individuals, as a binary value of present or absent.

The proportion of combined total and individual CV groups with present or absent T-cell responses will be reported.

The median (IQR) of T-cell responses (per 10⁶ PBMCs) will be reported in HC and 400 CV individuals. Multiple regression models will be fit to assess response, the following variables have been highlighted for inclusion in the model, using in the variables described in the serological models.

Pearson's Correlation or Spearman's Rank, as appropriate to the distribution. will be used to quantify the correlation between serological and cellular responses, in individual CV groups and combined group.

D) To evaluate cellular responses to new VOCs in CV patients

IFN ☐ reactivity in T-cells to variant spike peptides and compare this against reactivity to WT spike and expressed as fold change and absolute values for 2 time points 12 months apart.

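### The exploratory T-cell regressions carry no laboratory term, although in-person cells are processed in four laboratories and the ELISpot is placed in two

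*Protocol*

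**What the plan says.** **Laboratories.** Section 6.6 states "In-person samples will be transported to the local research laboratory at UoB, Southampton, Oxford or Imperial for processing". The cells are "Stored as peripheral blood lymphocytes to undertake T cell ELISpots and other exploratory studies". Section 9.3 describes the key test as "an established and standardised IFNy ELISpot assay (Oxford, Southampton"), so two of the four laboratories run it. Section 9.4 adds "Samples will be transferred between the laboratories for analysis during the study", and section 9.5 adds "A STRAVINSKY laboratory manual will be used to ensure standardised procedures across all 4 laboratories".

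**Models.** For T-cell responses, Appendix 3 C says "Multiple regression models will be fit to assess response" and continues "the following variables have been highlighted for inclusion in the model, using in the variables described in the serological models". The serological model is described with "The model will include the baseline variables set out in" Section 5.2. In this protocol that section is the inclusion criteria, so I read the reference as meaning the baseline list in Appendix 3. That list covers demographics, occupation and protective equipment, medical conditions, immunosuppression, vaccination history and prior infection. It names no laboratory and no site.

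**Reporting.** Appendix 3 C reports present/absent T-cell response for the combined total and for each clinical group. It reports medians for healthy controls and for the 400 in-person participants. Appendix 3 D compares reactivity to variant peptides with reactivity to wild-type spike, as fold change and as absolute values, at two time points.

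**The concern.** Processing laboratory follows the hospital a participant attends, and the assay is run in two places, so laboratory is a foreseeable source of measurement variation. Antibody is handled differently. Section 9.1 gives all participants one primary platform at Birmingham and compares it with other platforms against WHO reference serum. No comparable link between the two ELISpot laboratories is described.

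Two things are at stake. A level difference between laboratories goes into the residual and widens every interval in the T-cell regressions. If some clinical groups come mainly through one laboratory, part of that difference can also appear in the coefficients for medical condition and in the group proportions. T-cell response is a named fallback predictor should antibody fail, so comparability is best settled before the stored cells are assayed.

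**Working it through.** The documents give no figure for the T-cell analysis, so there is none to reproduce. The check traces the covariates and then illustrates the possible size.

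**1. Covariate trace.** T-cell regression (Appendix 3 C) → variables of the serological models → baseline list (Appendix 3). No laboratory or site appears at any step. The serological section allows variables to be added if evidence emerges that they affect vaccine response. A laboratory shift is a measurement effect, which that clause does not clearly cover.

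**2. Numbers per group.** 400 in-person participants over 20 groups (Table 2) average 400/20 = 20 per group. Spread evenly, that is 20/4 = 5 per processing laboratory or 20/2 = 10 per ELISpot laboratory. These are averages, because no in-person quota by group or site is stated.

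**3. Bias and error rate.** Let L be the shift between two laboratories in within-laboratory SDs, and s_A and s_B the shares of groups A and B handled in one of them. Then bias = L × (s_A − s_B). *Assumed:* L of 0.2, 0.5 or 1.0, and shares from even to fully separated. The error rates come from 20,000 simulated t tests (20 against 20, two-sided 5%, no true difference).

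| Shares, A v B | L = 0.2: bias; error | L = 0.5: bias; error | L = 1.0: bias; error |
|---|---|---|---|
| 50% v 50% | 0; 5.3% | 0; 4.5% | 0; 2.9% |
| 75% v 25% | 0.10 SD; 6.0% | 0.25 SD; 11.3% | 0.50 SD; 27.7% |
| 100% v 0% | 0.20 SD; 9.3% | 0.50 SD; 33.6% | 1.00 SD; 86.8% |

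**4. Variance under an even spread.** With half the samples in each laboratory, an unmodelled shift adds L² × 0.5 × 0.5 = L²/4 to a variance of 1. For L = 0.2, 0.5 and 1.0 the SD becomes √1.01 = 1.005, √1.0625 = 1.031 and √1.25 = 1.118. Intervals are then about 0.5%, 3.1% and 11.8% wider than they need be. This is also why the error rate at L = 1.0 falls below 5% in the even row.

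**5. With a laboratory term.** If the shift is additive on the model's scale, the term removes it from the contrast (bias 0), provided each group is spread over more than one laboratory. In the 100% v 0% row, group and laboratory are collinear and the term cannot separate them.

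**6. Analysis D.** If a laboratory multiplies counts by k, the variant/wild-type ratio is kV/kW = V/W, so a proportional effect cancels. The absolute value kV does not cancel.

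**The case against.** The protocol calls the ELISpot standardised and puts one manual over all four laboratories. It leaves sample transfer and distribution to that manual, which is not at hand, so a sensible assignment rule may already exist. Cells from Birmingham and Imperial must travel to be assayed, so hospital does not by itself fix the ELISpot laboratory. The analyses are exploratory, and a laboratory covariate is the sort of detail a fuller analysis plan could add.

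Much of this stands, and it rules out several stronger readings that a reader might infer:

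- *Laboratory differences will be reported as group differences.* That needs both a real shift and an uneven spread. The documents show neither.
- *Fold changes between visits may be laboratory changes.* The fold change in D is variant against wild type. Each in-person participant also attends one site for all four visits, so the processing laboratory is normally constant within a person.
- *Group medians are biased.* Medians are planned for controls and for the 400 together, not by group.
- *The error rates above are those of a planned test.* Appendix 3 C describes no such test between groups.
- *Nothing keeps a participant's time points in one laboratory.* That cannot be established without the manual.

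The objection does not remove the omission. A manual standardises procedure, but it neither shows equal levels nor adjusts for unequal ones. Section 11 names Appendix 3 as the statistical analysis plan, and Appendix 3 does name the covariates, without laboratory among them.

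**Conclusion.** The point holds as a minor one. The covariate set fixed for the T-cell regressions omits a foreseeable source of measurement variation. The certain part is that any level difference between laboratories goes unmodelled and adds variance: about 3% on interval width for an assumed 0.5 SD shift evenly split. Confounding with clinical group is only possible. It ranges from zero under an even spread to the full shift under complete separation, and the documents do not say where the study lies between these. No primary or secondary result depends on it.

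**What to change.** In Appendix 3 C, add processing laboratory and ELISpot laboratory as covariates in the T-cell regressions, and show the present/absent proportions by clinical group also by ELISpot laboratory. In D, apply the same term to the absolute values where they are modelled, or show them by laboratory where they are only described. The variant/wild-type fold change needs it less.

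The laboratory is known for each sample, since section 9.4 keeps the sample record in each laboratory's information system. The cost is wording plus (4 − 1) + (2 − 1) = 4 degrees of freedom out of 400 participants. If each processing laboratory always sends to the same ELISpot laboratory, the second term is redundant and the cost is three. Where a group lies wholly in one laboratory, its effect cannot be separated from the laboratory effect, and the report should say so.

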4.2 Objectives

Primary objectives:

a) To define and assess the predictive value of SARS-CoV-2 spike serology measurements for COVID-19 clinical outcomes (infection rates and disease severity) in CV people.

Secondary objectives:

- a) To evaluate the serological vaccine responses (magnitude and durability) of CV patients to bivalent or other vaccines given during the study period.
- b) To assess the functional activity of anti-spike IgG antibodies against new SARS-CoV-2 variants in CV patients during the study period.

Exploratory objectives:

- a) To evaluate alternate methods to predict COVID-19 infection/hospitalisation should antibody testing fail to predict relevant clinical outcomes (e.g. QCOVID4 score and T cell responses).
- b) To understand whether the serology vaccine response, in those with suboptimal responses to primary course, can be further enhanced with increasing doses of vaccination. \Box
- c) To assess T-cell response to emerging VoC in CV individuals.
- d) To determine the correlation between antibody and T-cell responses

Version: 2.0 26.11.2023 IRAS:325967

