If a participant belongs to more than 1 disease/treatment group, allocation will follow the following prioritisation:

Does the patient fit into any of the treatment-related groups?

Yes —> allocation to Treatment-related group. Patients should be preferentially allocated to the first treatment-related group that can be applied to them in the list above from rows 15 to 20 above.

No -> allocation to disease-related group that is considered by the local clinical investigator to be the MAIN disease. Patients should be preferentially allocated to the first disease-related group that can be applied to them in the list above from rows 1-14 above.

Footnotes:

- 1. Any chronic/indolent/low-grade B or T-cell lymphoproliferative disorder e.g. follicular lymphoma, chronic lymphocytic leukaemia, lymphoplasmacytic lymphoma etc.
- 2. e.g. myeloma, plasma cell leukaemia and AL amyloidosis and excluding monoclonal gammopathy of undetermined significance (MGUS).
- 3. Includes myelodysplastic syndrome, myeloproliferative neoplasms, myelofibrosis and chronic myelomonocytic leukaemia.
- 4. Any rare neurological and severe complex neurodisability e.g. multiple sclerosis, motor neurone disease, myasthenia gravis, Huntingdon's disease, and also Parkinson's disease.
- 5. Cirrhosis Child-Pugh class A, B and C.
- 6. Chronic obstructive pulmonary disease, Interstitial Lung disease, Pulmonary hypertension
- 7. eGFR less than 30 ml/min/1.73m²

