6.0 Prospective study

6.1 Study design and overview

This is a multicentre prospective, observational cohort study (**FIGURE 1**). Patients will provide samples and clinical data on 4 different occasions over 12-18 months. For each of the 4 visits individuals will be allocated to be involved in the study either remotely or attend in-person.

3000 individuals will be recruited in total; for 2600 of these patients (remote cohort), their commitment to the study will be entirely remote.

400 individuals (in-person cohort) will be invited to attend a sampling appointment at one of the 4 inperson sampling sites (Birmingham, Southampton, Imperial or Oxford), for each of the 4 study visits. The aim will be to recruit between 120 and 140 individuals per disease/treatment group as detailed in **TABLE 2.**

13 | Page STRAVINSKY Protocol

^{*} This enables assessment of the primary outcome and response to bivalent vaccine. It is highly likely that policy on these licensed treatments will change, in which case we may submit an amendment to individuals receiving SARS-CoV-2 monoclonal Abs.

Informed consent and data collection will predominantly be collected online via a REDCap database. Patients and sites without access to devices or internet will be consented via telephone, the signed paper consent form will then be sent to the participant to counter sign, and they will be asked to post this back to the central study team.

Participants without access to devices to internet will also be offered face to face appointments where the patient can either be supported by the research nurse to complete the online consent form or the participant can sign a paper consent form. If paper consent forms are used, they will be transcribed/scanned into REDCap and the original paper source document will be stored at the recruiting site for the duration of the study. Any case report form (CRF) data collected face to face or via telephone will also be transcribed directly into the database by each local clinical care team. Paper CRF data and consent forms will be transcribed/scanned into REDCap. The original paper documents will be stored at the recruiting site.

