- · Occupation, nature of work and type of personal protective equipment used during that work
- Medical conditions (self- reported)
- latrogenic immunosuppression (or within 6 months of iatrogenic immunosuppression including chemotherapy)
- · Vaccination history including COVID-19, influenza, and any test vaccines given
- · Known prior infection

Behavioural variables

If the participant self-isolated as a result of an illness in a household contact, we will collect data on the nature of that illness (when was illness, symptoms, severity, duration) and how many other household contacts were unwell.

Serological response

Time points for serological measurements: Assessment at 4 timepoints (Visit 1: baseline visit, Visit 2: before next vaccine dose, visit 3: 4 weeks post vaccine dose and Visit 4: 24-36 weeks post vaccine).

ii) 'Low' antibody range: Antibody values which lie within the lower 10th percentile of range of IgG antibody concentrations in HC following vaccine dose.

General analysis principles

- Summary statistics will include either mean, standard deviation, and/or median, interquartile range for continuous variables as appropriate to the distribution and n (%) for frequencies.
- The amount of missing data will be reported. Analysis will be of complete data and missing data will not be imputed.
- 5% two-sided level of statistical significance, with corresponding 95% confidence intervals presented where applicable.
- No adjustments for multiplicity are planned.

Planned analyses and reporting:

Primary Outcome

To assess the additive value of serological responses to CV status in predicting infection

The binary infection outcome will be captured by recording the timing and incidence rates of all infections from ≥14 days post vaccination given between Visit 2 until Visit 4 will be reported in the total combined CV groups, and by individual CV groups. We will describe the number and proportion of infections for each level of antibody response post-V3 (no, low, normal)

The primary analysis will be undertaken using a logistic regression model with infection as the outcome and antibody response post-V3 as a binary variable as the exposure. We will present odds ratios with 95% confidence intervals for the unadjusted model, as well as for a model adjusted for the baseline and behavioural variables as well as any COVID-19 therapy received in the community, preadmission and in hospital (where data available).

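### The planned antibody/T-cell correlations leave out a pooled within-group estimate: single-group coefficients (about 20 people each) are imprecise, and the raw combined one mixes within-group and between-group association

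*Protocol*

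**What the plan says.** Exploratory objective (d) in Protocol section 4.2 is "To determine the correlation between antibody and T-cell responses". It does not say whether the correlation is meant within disease groups or across the whole cohort.

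The sampling table in section 6.6 gives the source of T-cell data. Under "In-person sampling (n=400" the cells are "Stored as peripheral blood lymphocytes to undertake T cell ELISpots and other exploratory studies". The remote cohort gives only dried blood spots. Appendix 3 C accordingly states that "T-cell responses will be reported in HC and 400 CV individuals, as a binary value of present or absent", at Visit 3.

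For the correlation itself, Appendix 3 C says that Pearson's or Spearman's coefficient "will be used to quantify the correlation between serological and cellular responses, in individual CV groups and combined group". No partial, stratified or group-adjusted coefficient is named. The same part plans multiple regression of T-cell response on the variables of the serological models, but antibody level is not named as a predictor.

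Table 2 in section 5.1 has 20 groups; the treatment-related ones are "in the list above from rows 15 to 20 above". Section 6.1 says "The aim will be to recruit between 120 and 140 individuals per disease/treatment group". That target covers the full 3000. No target per group is stated for the in-person cohort.

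**The concern.** T-cell response is the first alternative listed in Appendix 3 B should antibody fail to predict outcome. For that purpose a useful question is whether, among people with the same condition or treatment, those with low antibody also have a low T-cell response.

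Neither named estimate answers this well alone. A single group coefficient rests on about 20 people. The combined coefficient rests on up to 400, but it adds two things together: the relation inside groups and the relation between group means. The groups run from B-cell depletion and stem cell transplant to diabetes and cardiac failure, and section 2.0 describes vaccine response in disease populations as heterogeneous. If group means differ for both markers, the combined coefficient partly reflects which groups were sampled and in what proportions.

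The stake is the interpretation of one exploratory objective. A reader could take the combined coefficient as evidence about patients within a group, or could over-read whichever of the 20 group coefficients happens to be large.

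**Working it through.** **The plan's own figures.** The documents give no precision or power figure for this correlation. The only power statement in Appendix 3 concerns the whole-cohort comparisons of infection and hospitalisation. Its lowest infection effect size, 0.15, reproduces: with 750 v 2250 and 90% power, 50% v 56.8% is detectable, and ln(OR)·√3/π = 0.151. It has no bearing on the correlation.

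**Inputs.** In-person n = 400 (section 6.6). Groups = 20 (Table 2). The significance rule is "5% two-sided level of statistical significance, with corresponding 95% confidence intervals presented where applicable", with complete data only and no multiplicity adjustment (Appendix 3, general analysis principles). Values of r are illustrative.

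**Size per group.** 400 / 20 = 20, an average under an even spread, which the documents do not promise. Complete-case analysis lowers the usable number. So may Appendix 6, where in-person participants recruited after the booster, or declining it, have no visit labelled Visit 3.

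**Precision of one group coefficient.** Fisher's z: SE = 1/√(n - 3) = 1/√17 = 0.2425.

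- r = 0.4: atanh(0.4) = 0.4236; 0.4236 ± 1.96 × 0.2425 = -0.052 to 0.899; back-transformed, **-0.05 to 0.72**. Power = Φ(0.4236/0.2425 - 1.96) = Φ(-0.21) = **42%**.
- r = 0.3: -0.16 to 0.66; power 25%. With Spearman's variance (1 + r²/2)/(n - 3), about -0.18 to 0.66.
- 80% power needs r of about 0.59.
- With 16 usable per group (an assumed 20% loss), r = 0.3 gives -0.23 to 0.69.

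**Reading 20 coefficients one by one.** With every true r = 0 and independent tests, the chance of at least one p < 0.05 is 1 - 0.95²⁰ = 64%. In simulation, with every true r = 0.3, the 20 estimates run on average from about -0.14 to 0.64.

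**What the combined coefficient measures.** If a share k of each marker's variance lies between groups, then r(combined) = k·r(between) + (1 - k)·r(within). The documents give neither k nor r(between). Assume k = 0.10 to 0.30 and r(between) = -0.8 to 0.8. The extremes fall at k = 0.30:

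| Within-group r | r(between) = -0.8 | r(between) = 0.8 |
|---|---|---|
| 0 | 0.3 × (-0.8) = **-0.24** | 0.3 × 0.8 = **0.24** |
| 0.3 | -0.24 + 0.7 × 0.3 = **-0.03** | 0.24 + 0.21 = **0.45** |

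At k = 0.10 the effect is small: a within-group r of 0 appears as -0.08 to 0.08.

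**Pooled within-group estimate, same 400 people, r = 0.4.**

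- Partial correlation with 19 group terms: SE = 1/√(400 - 3 - 19) = 0.0514; interval 0.31 to 0.48.
- Fisher-z average of the 20 group coefficients: SE = 1/√(20 × 17) = 0.0542; interval 0.31 to 0.49.
- Raw combined coefficient, for comparison: SE = 1/√397 = 0.0502; interval 0.31 to 0.48.

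Removing the between-group part costs almost no precision.

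**The case against.** The strongest reply is that nothing in the plan is an error. Each part of it has force.

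- **The list of analyses is open.** The sentence leading into Appendix 3 C says that the assessment is not confined to what follows. A reader might infer that the plan restricts itself to the two named kinds of coefficient. It does not: a group-adjusted one is unnamed, not excluded.
- **Neither coefficient is ranked.** A reader might take the combined coefficient as the main estimate for objective (d). The text sets it beside the group coefficients and gives neither priority.
- **The combined coefficient is valid for what it describes.** Objective (d) asks for no within-group or adjusted relation, so calling the combined value confounded presumes a target that the document does not set. It can differ from the within-group relation; whether it does, and in which direction, cannot be derived from the documents.
- **The 20 coefficients already hold the within-group information.** Taken singly they are weak. Averaged, they give the precision shown above. Only the summary is missing.

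All four points stand, and they limit the finding to an improvement. They do not remove it: the within-group summary is not named, both named estimates can mislead on the within-group question, and the regression planned in the same part is not stated to include antibody.

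**Conclusion.** The point holds as a minor improvement to an exploratory analysis. Appendix 3 C names group coefficients that are each imprecise (-0.05 to 0.72 at r = 0.4 with 20 people) and a combined coefficient that mixes two kinds of association. It does not name the pooled within-group estimate, which would be nearly as precise as the combined one.

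The conclusion rests on an average of 20 per group, which assumes an even spread; with an uneven spread some groups are smaller and others larger. The possible gap between combined and within-group values (0 appearing as -0.24 to 0.24; 0.3 appearing as -0.03 to 0.45) is an illustration under assumed variance shares, not an estimate for this cohort. The pooled value also assumes a broadly common within-group correlation; if groups differ, it is an average over them.

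The documents do not support the stronger conclusion that the planned combined correlation is biased by a known amount or must be dropped. The primary analysis and the secondary objectives are unaffected.

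**What to change.** In Appendix 3 C, add a pooled within-group estimate of the antibody/T-cell correlation for exploratory objective (d), and state that the objective will be interpreted mainly on it. Either a partial Pearson or Spearman correlation adjusted for CV group, or a Fisher-z pooling of the group coefficients, would serve. Name one in advance.

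Keep the raw combined coefficient, labelled as a description of this cohort. Keep the 20 group coefficients as descriptive, each with its number of participants and 95% interval.

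The cost is a few lines of wording. No new data, samples or visits are needed.
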